### 1.1 Study design

This is a Phase 2, multi-part, multi-center, open-label platform study including CCI

This platform design allows the potential to investigate multiple therapies in the context of a single disease. Each anti-malarial agent entered in the trial at a given time will follow the same design as outlined in Parts A, B, and C. More than one Part A, Part B, and Part C cohort can be conducted at the same time. In addition, Part A, Part B, and Part C cohorts can be conducted at the same time.

CCI

CCI

**Part A** is the open-label, randomized, multi-arm monotherapy part of this Phase 2 study evaluating a single oral administration of an anti-malarial agent at 3 parallel dose levels followed by optional adaptive sequential dose level(s).

CCI

**Part B** is the open-label, randomized, two-arm combination therapy part of this Phase 2 study evaluating a single oral dose of up to three anti-malarial agents as a loose combination vs. standard of care (SoC), Coartem in adult and adolescent patients.

CCI

CCI

**Part C** is the open-label, randomized, two-arm combination therapy part of this Phase 2 study evaluating a single oral dose of up to three anti-malarial agents as a loose and/or fixed combination vs. SoC, Coartem, in children aged 2 to < 12 years.

CCI

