## 2 Statistical methods

### 2.1 Data analysis general information

Unless otherwise noted, by default all outputs will be presented by cohort (e.g. A1, B1, B2, C2) and treatment group within each cohort. Data from common treatment groups and/or doses may be pooled at a later time. *In the following sections, “by cohort and treatment group” is thus removed as it applies to all outputs.*

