### **2.7.4 Other safety data**

#### **2.7.4.1 ECG and cardiac imaging data**

PR, QRS, QT, QTcF, and RR intervals will be obtained from 12-lead ECGs. ECG data will be read and interpreted (local and centrally). Local readings will be used only for site decision making purposes and not for any analyses; only central readings will be used for the summaries and listings described below.

When ECG triplicates are collected at any assessment, the average of the ECG parameters at that assessment will be used in the analyses.

Categorical analysis of QT/QTc interval data based on the number of patients meeting or exceeding predefined limits in terms of absolute QT/QTc intervals or changes from baseline will be presented.

The number and percent of patients with notable ECG values will be presented.

- QT, QTcF
  - New value of  $> 450$  and  $\leq 480$  ms
  - New value of  $> 480$  and  $\leq 500$  ms
  - New value of  $> 500$  ms
  - Increase from baseline of  $> 30$  ms to  $\leq 60$  ms
  - Increase from baseline of  $> 60$  ms
- HR (= 60/RR (sec)) for age  $\geq 18$  years
  - Increase from baseline  $>25\%$  and to a value  $> 100$  bpm
  - Decrease from baseline  $>25\%$  and to a value  $< 50$  bpm
- HR (= 60/RR (sec)) for age  $< 18$  years
  - $> 90$ th percentile defined in [Table 2-2](#)
  - $< 10$ th percentile defined in [Table 2-2](#)
- PR
  - Increase from baseline  $>25\%$  and to a value  $> 200$  ms
  - New value of  $> 200$  ms
- QRS
  - Increase from baseline  $>25\%$  and to a value  $> 120$  ms
  - New values of QRS  $> 120$  ms

ECG data will be summarized by presenting summary statistics of observed data and change from baseline by time point.

A listing will be provided for patients with any notable values defined above. If there is any notable value of an ECG for a patient, all measurements of this ECG value for the patient will be presented in this listing with the notable values flagged. A summary and listing will also be provided of ECG findings for which there is a clinically significant ECG abnormality.

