**Table 2-2 Heart rate cut-offs (bpm) for 2 to  $<18$  years based on centile charts**

Age Range	10 th percentile	90 th percentile
2 - $<3$	92	128
3 - $<4$	86	123
4 - $<6$	81	117
6 - $<8$	74	111
8 - $<12$	67	103
12 - $<15$	62	96

Age Range	10 th percentile	90 th percentile
15 – <18	58	92

Reference: Lancet. 2011 March 19; 377(9770): 1011–1018. doi:10.1016/S0140-6736(10)62226-X.

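### The notable PR and QRS categories use one limit at all ages with no stand-alone change category, so the patient-level count may miss sizeable prolongation in Part C children

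*SAP*

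**What the plan says.** SAP 2.7.4.1 lists the ECG values to be counted as notable.

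- **Heart rate** is split at 18 years. Adults have fixed limits combined with a change from baseline. Younger patients are compared with the 10th and 90th percentiles of Table 2-2, whose title begins "Heart rate cut-offs (bpm) for 2 to" and whose limits are "based on centile charts".
- **PR** has two rules and no age split: "Increase from baseline $>25\%$ and to a value $> 200$ ms", and any new value above 200 ms.
- **QRS** has the same structure: "Increase from baseline $>25\%$ and to a value $> 120$ ms", and "New values of QRS $> 120$ ms".
- **QT and QTcF** have absolute categories and also separate categories for an increase of more than 30 up to 60 ms and of more than 60 ms. Those increases count whatever value is reached.

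The listing of patients with notable values uses the same definitions. The section also plans descriptive statistics of ECG change from baseline at each time point, and a summary and listing of clinically significant ECG abnormalities.

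These rules reach young children. SAP 1.1 describes Part C as a comparison with Coartem "in children aged 2 to < 12 years", and SAP 2.1 states that "by default all outputs will be presented by cohort (e.g. A1, B1, B2, C2) and treatment group within each cohort". SAP 3.2.3 plans 80 evaluable children on KLU156+cipargamin and 40 on Coartem in Cohort C2.

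**The concern.** The SAP accepts that adult limits do not suit children for heart rate, pulse and blood pressure (Tables 2-2 and 2-3, Section 5.4), but does not carry this over to the conduction intervals in the same list. If children start from shorter intervals than adults, a fixed limit asks a child for a larger proportional rise before the child is counted. The 25% rule looks as if it would deal with this. It does not, because it is tied to the same limit.

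At stake is the table giving the number and percent of patients with notable ECG values, and the listing built on it. For the youngest participants, that table could show few PR or QRS entries although a number of children had a sizeable rise.

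**Working it through.** **Inputs.** From SAP 2.7.4.1: PR limit 200 ms, QRS limit 120 ms, relative condition >25%. From SAP 3.2.3: 80 children on the combination. The documents give no paediatric PR or QRS values, so every baseline below is an assumption. The plan states no figure to reproduce here.

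**Step 1: does the 25% rule add anyone?** Read a new value as one above the limit in a patient whose baseline was not; the SAP does not define the term. If baseline PR is at most 200 ms and a later value is above 200 ms, that value is already new. So the rule combining >25% with >200 ms adds no patient. A grid check agrees: 0 added cases with baseline at or below 200 ms. The rule adds patients only when baseline already exceeds the limit. The same logic holds for QRS at 120 ms.

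**Step 2: from what baseline is a rise just over 25% flagged?** Baseline = limit / 1.25.

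- PR: 200 / 1.25 = 160 ms
- QRS: 120 / 1.25 = 96 ms

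**Step 3: what rise is needed from a shorter baseline?** Required rise = limit / baseline − 1.

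| Assumed PR (ms) | Rise needed | Assumed QRS (ms) | Rise needed |
|---|---|---|---|
| 100 | >100% | 60 | >100% |
| 120 | >66.7% | 70 | >71.4% |
| 140 | >42.9% | 80 | >50.0% |
| 160 | >25.0% | 96 | >25.0% |

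For example, a child whose PR goes from 120 to 190 ms (190 / 120 − 1 = +58%) enters neither the count nor the notable-value listing.

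**Step 4: how many of 80 children would be flagged?** Suppose every child's interval rises by the same proportion r and baselines are normal, with assumed SD 15 ms (PR) and 8 ms (QRS). The share flagged is 1 − Φ((limit/(1+r) − mean)/SD). For PR with mean 120 and r = 0.50: 200/1.5 = 133.3; (133.3 − 120)/15 = 0.889; share 0.187; 80 × 0.187 = 15.

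| Interval, assumed mean (ms) | Flagged of 80, r = 26% | Flagged of 80, r = 50% |
|---|---|---|
| PR 110 | 0.05 | 4.8 |
| PR 120 | 0.4 | 15 |
| PR 140 | 8.5 | 54 |
| QRS 60 | 0.0 | 0.5 |
| QRS 70 | 0.06 | 8.5 |
| QRS 80 | 2.3 | 40 |

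A stand-alone >25% category would count all 80 in every row. The shortfall is large for moderate rises. For large rises it depends heavily on the baseline assumed.

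**Step 5: would the averages show it?** A shift in all children would appear in the mean change. A rise in a few would be diluted: if 4 of 80 rose by 60 ms, the mean moves by 4 × 60 / 80 = 3 ms.

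**The case against.** The strongest reply is that the notable-value table is only one of several ECG outputs. Change-from-baseline statistics are planned by time point and, under SAP 2.1, by cohort and arm, so a systematic PR or QRS shift would show against randomised Coartem. Clinically significant abnormalities have their own summary and listing, not tied to 200 or 120 ms, and conduction events reported as adverse events are tabulated. All of this stands. It limits the point to the patient-level count and its listing. It does not close the gap, because averages do not give the number of children affected and the SAP sets no criterion for clinical significance.

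Three further replies also hold in part.

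- The gap is not peculiar to children. Any adult with PR below 160 ms or QRS below 96 ms also needs more than a 25% rise, and the adult heart-rate rules have the same joined form.
- That children have shorter intervals is not stated in the documents. Table 2-2 gives heart rate only.
- A bare 25% rule could flag recovery. Baseline is taken during acute malaria, and PR may lengthen as heart rate settles (an assumption). Averaging triplicates reduces noise but not such a shift. The Coartem arm gives a reference for it.

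A reader might infer that large conduction slowing in children goes uncounted, that Cohort C2 would report almost no notable values even under a substantial effect, or that its cardiac safety conclusion would be falsely reassuring. The documents do not support these readings: very large rises are still flagged, as the 50% column shows, and the other outputs remain. Nor does the protocol's exclusion of clinically significant AV block (Section 5.2) show that any study drug slows conduction; it is a general eligibility criterion.

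**Conclusion.** The point holds for the notable-value count and its listing. PR and QRS are not age-adjusted and, unlike QT/QTcF, have no stand-alone change category. For any baseline at or below the limit, the 25% condition adds nobody. A rise of just over 25% is flagged only from a PR of at least 160 ms or a QRS of at least 96 ms; this follows from the SAP's own numbers. How many children are missed rests on assumed baselines: with a uniform 26% rise, the rules would flag about 0.05 to 8.5 of 80 for PR and about 0 to 2.3 of 80 for QRS. Adolescents in Part B may be affected to a lesser degree.

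One limit applies. The supplied protocol has no Part C, and the SAP refers to protocol version 03, so any ECG rules for Part C in that version could not be checked. The change is a cheap improvement; the ECG safety evaluation as a whole does not fail without it.

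**What to change.** For patients under 18 years, keep the current PR and QRS categories in SAP 2.7.4.1 and add one reporting category for each interval: an increase from baseline of more than 25%, whatever value is reached. Alternatively, use age-specific upper limits with a cited source, as Table 2-2 does for heart rate; the documents do not supply such limits. Present the counts by arm against Coartem and extend the notable-value listing to match. Adult categories stay as they are. This is a reporting category only and implies nothing about clinical management.

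The cost is a short SAP amendment and one programming condition per interval, using central ECG readings already planned. The downside is some extra flags from measurement noise or from heart rate falling as patients recover, which is why the counts should be read against the Coartem arm.

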**Table 2-2 Heart rate cut-offs (bpm) for 2 to  $<18$  years based on centile charts**

Age Range	10 th percentile	90 th percentile
2 - $<3$	92	128
3 - $<4$	86	123
4 - $<6$	81	117
6 - $<8$	74	111
8 - $<12$	67	103
12 - $<15$	62	96

Age Range	10 th percentile	90 th percentile
15 – <18	58	92

Reference: Lancet. 2011 March 19; 377(9770): 1011–1018. doi:10.1016/S0140-6736(10)62226-X.

### 2.7.4.2 Vital signs

Summary statistics will be provided by visit/time.

The number and percent of patients with newly occurring notable vital signs will be presented; for Part B they will be separated by <18 years ([Table 2-3](#)) and ≥18 years ([Table 2-4](#)).

**Table 2-3 Criteria for notably abnormal vital signs for 2 to <18 years (Parts B & C)**

Vital sign		Criteria	
Systolic blood pressure [mmHg]	High	≥ 95 th percentile of the age and height group 	
	Low	≤ 5 th percentile of the age and height group 	
Diastolic blood pressure [mmHg]	High	≥ 95 th percentile of the age and height group 	
	Low	≤ 5 th percentile of the age and height group 	
Body temperature [°C]	High	≥ 37.5°C ( axillary equivalent )	
Pulse rate [bpm] 	High	2-<3 years	> 128
		3-<4 years	> 123
		4-<6 years	> 117
		6-<8 years	> 111
		8-<12 years	> 103
		12-<15 years	> 96
		≥ 15 years	> 92
	Low	2-<3 years	< 92
		3-<4 years	< 86
		4-<6 years	< 81
		6-<8 years	< 74
		8-<12 years	< 67
		12-<15 years	< 62
		≥ 15 years	< 58

 Fourth Report on Diagnosis, Evaluation and Treatment of High Blood Pressure in Children and Adolescents. Pediatrics 2004; 114; 555 (see [Section 5.4](#) for detailed computation)

[\[Body mass index-for-age \(BMI-for-age\) \(who.int\)\]](#)

**Table 2-4 Criteria for notable vital sign abnormalities for ≥18 years (Parts A & B)**

Vital sign	Notable abnormalities
Systolic blood pressure	≥180 mmHg and increase ≥20 mmHg ≤ 90 mmHg and decrease ≥20 mmHg
Diastolic blood pressure	≥105 mmHg and increase ≥15 mmHg ≤ 50 mmHg and decrease ≥15 mmHg
Pulse rate	≥100 bpm with increase >25% ≤50 bpm with decrease >25%

Vital sign	Notable abnormalities
Temperature	$\geq 37.5$ (axillary) or $\geq 38.0$ (other routes) °C

Listing of patients with notable vital signs will be provided. If there is any notable value for a patient, all measurements of this vital sign for the patient will be presented with the notable values flagged.

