8.4.6 Other safety evaluations

Signs and symptoms of severe malaria

Danger signs:

- not able to drink
- vomiting > twice within preceding 24 hours
- one convulsion within preceding 24 hours
- unconscious state
- unable to sit or stand

Signs of severe malaria:

Severe *P. falciparum* malaria is defined as one or more of the following, occurring in the absence of an identified alternative cause and in the presence of *P. falciparum* asexual parasitemia:

- Impaired consciousness (Glasgow coma score < 11 in adults)
- Prostration (generalized weakness i.e., unable to sit, stand or walk without assistance)
- Multiple convulsions (more than two episodes within 24 hours)
- Acidosis (a base deficit of > 8 mEq/L or if not available a plasma bicarbonate level of < 15 mmol/L or venous plasma lactate \geq 5 mmol/L. Severe acidosis manifests clinically as respiratory distress i.e., rapid, deep, labored breathing)
- Hypoglycemia (blood or plasma glucose < 2.2 mmol/L; < 40 mg/dL)
- Severe malarial anemia (hemoglobin concentration \leq 5 g/dL or a hematocrit of \leq 15% in children < 12 years of age (< 7 g/dL and < 20% respectively in adults) with a parasite count > 10,000/ μ L)
- Renal impairment (plasma or serum creatinine > 265 μ mol/L (3 mg/dL) or blood urea > 20 mmol/L)
- Jaundice (plasma or serum bilirubin > 50 μ mol/L (3 mg/dL) with a parasite count > 100,000/ μ L)
- Pulmonary edema (radiologically confirmed or oxygen saturation < 92% on room air with a respiration rate > 30/min, often with chest indrawing and crepitation on auscultation)
- Significant bleeding (including recurrent or prolonged bleeding from the nose, gums of venipuncture sites, hematemesis or melena)
- Shock (compensated shock i.e., capillary refill \geq 3s or temperature gradient on leg but no hypotension; decompensated shock i.e., systolic blood pressure < 70 mm Hg in children or < 80 mm Hg in adults with evidence of impaired perfusion)
- Hyperparasitemia (*P. falciparum* parasitemia > 10%)

If a patient experiences and danger signs / signs of severe malaria, the investigator should report the event as an SAE following the guidance provided in [Section 8.6.3](#). Local guidance should be followed for the treatment of these danger signs / signs of severe malaria.

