## 5.4 Computation of Blood Pressure Percentiles for Arbitrary Sex, Age, and Height

The below algorithm is described in Appendix B of the following reference: The Fourth Report on Diagnosis, Evaluation and Treatment of High Blood Pressure in Children and Adolescents. Pediatrics 2004; 114; 555.

- To compute the systolic blood pressure (SBP) percentile of a boy whose age is  $y$  years and height =  $h$  inches with SBP =  $x$  mmHg:
  - Convert the height of  $h$  inches to a height Z-score relative to boys of the same age (as per data tables provided in [Table 5-8](#)); this is denoted by  $Z_{ht}$ .
  - Compute the expected SBP ( $\mu$ ) for boys of age  $y$  years and height  $h$  inches given by

$$\mu = \alpha + \sum_{j=1}^4 \beta_j (y - 10)^j + \sum_{k=1}^4 \gamma_k (Z_{ht})^k$$

where, regression coefficients are given in the 3rd column of [Table 5-7](#).

- Then convert the boy's observed SBP ( $x$ ) to a Z-score ( $Z_{BP}$ ) given by

$$Z_{BP} = \frac{(x - \mu)}{\sigma}$$

where,  $\sigma$  is given in the 3rd column for standard deviation row of [Table 5-7](#).

- To convert the bp Z-score to a percentile (P), compute  $P = \Phi(Z_{BP}) \times 100\%$   
where  $\Phi(Z)$  = area under a standard normal distribution to the left of Z.
- Likewise, to compute percentiles for SBP for girls, diastolic blood pressure (DBP) (K5) for boys, and DBP (K5) for girls, use the regression coefficients from the 4th, 5th, and 6th columns of [Table 5-8](#).

For example, a 12-year-old boy with height at the 90th percentile for his age-sex group has a height Z-score = 1.28, and his expected SBP ( $\mu$ ) is

$$\begin{aligned} \mu = & 102.19768 + 1.82416 (2) + 0.12776 (2^2) + 0.00249 (2^3) - 0.00135 (2^4) + 2.73157 \\ & (1.28) - 0.19618 (1.28^2) - 0.04659 (1.28^3) + 0.00947(1.28^4) = 109.46 \text{ mmHg.} \end{aligned}$$

**Table 5-7 Regression coefficients from Blood Pressure Regression Models****Regression Coefficients From Blood Pressure Regression Models\***

Variable Name	Symbol	Systolic BP		Diastolic BP5	
		Male	Female	Male	Female
Intercept	$\alpha$	102.19768	102.01027	61.01217	60.50510
Age					
Age-10	$\beta_1$	1.82416	1.94397	0.68314	1.01301
(Age-10) 	$\beta_2$	0.12776	0.00598	-0.09835	0.01157
(Age-10) 	$\beta_3$	0.00249	-0.00789	0.01711	0.00424
(Age-10) 	$\beta_4$	-0.00135	-0.00059	0.00045	-0.00137
Normalized height					

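### The SAP's low systolic flags have no absolute floor, so some new readings below 80 mmHg in adults (and below 70 mmHg in short children of about 2 to 4 years) are not counted as notable

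*SAP*

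**What the plan says.** **Adults.** SAP Table 2-4 (18 years and over, Parts A and B) has one criterion for low systolic pressure: "≤ 90 mmHg and decrease ≥20 mmHg". It has no category based on level alone.

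**Ages 2 to under 18.** SAP Table 2-3 calls systolic pressure low at or below the 5th "percentile of the age and height group". SAP 5.4, "Computation of Blood Pressure Percentiles for Arbitrary Sex, Age, and Height", gives the formula and coefficients. The SAP describes Part C as enrolling "in children aged 2 to < 12 years".

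**Reporting.** SAP 2.7.4.2 says: "The number and percent of patients with newly occurring notable vital signs will be presented". The text under Table 2-4 adds: "Listing of patients with notable vital signs will be provided". A patient with no notable value is in neither output. Protocol 9.4.2 is wider: it plans a listing of all vital signs by patient and visit, with abnormalities flagged where ranges exist.

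**Protocol reference values.** Among the signs of severe malaria, protocol 8.4.6 describes decompensated shock as "systolic blood pressure < 70 mm Hg in children or < 80 mm Hg in adults with evidence of impaired perfusion".

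**Precedent in the SAP.** For PR and QRS, SAP 2.7.4.1 pairs a change-plus-level criterion with a separate criterion for any new value above an absolute limit. Blood pressure has no such companion.

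**The concern.** Baseline is the last pre-dose value, taken during acute malaria, when pressure may already be low. The exclusion criteria in protocol 5.2 set no minimum systolic pressure. Requiring a 20 mmHg fall means that the lower a patient starts, the lower a reading must go before it counts. In young children the percentile limit has a similar effect, because it falls with age and height and nothing stops it.

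The table of notable values exists to count measured values without relying on an investigator's judgement. If it omits new readings below the level that the protocol uses within its own shock definition, a comparison of arms on low blood pressure after dosing is incomplete for the patients with least reserve. A low reading without documented impaired perfusion need not become a severe-malaria SAE, so this table is where one would look for it.

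**Working it through.** **1. Adult flag.** Input: Table 2-4. A reading x from baseline b is flagged if x ≤ 90 and b − x ≥ 20, that is, if x ≤ min(90, b − 20). Compare with x < 80, in whole mmHg:

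| Baseline | Highest flagged reading | Readings below 80 not flagged |
|---|---|---|
| 85 | 65 | 66–79 |
| 90 | 70 | 71–79 |
| 95 | 75 | 76–79 |
| 98 | 78 | 79 |
| 99 | 79 | none |
| 110 | 90 | none |

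The gap exists for baselines of 80 to 98 and always involves a fall of 1 to 19 mmHg. Any fall of 20 mmHg or more that ends at 90 or below is flagged.

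**2. Adults exposed.** The documents give no baseline systolic distribution. Assume it is normal and take P(baseline < 98.5), which is a baseline of 98 or lower in whole mmHg:

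| Mean | SD 10 | SD 12 | SD 15 |
|---|---|---|---|
| 105 | 25.8% | 29.4% | 33.2% |
| 110 | 12.5% | 16.9% | 22.2% |
| 115 | 4.9% | 8.5% | 13.6% |
| 120 | 1.6% | 3.7% | 7.6% |

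**3. Paediatric formula, reproducing the SAP's figure.** The worked example in SAP 5.4 (boy of 12, height Z 1.28) begins "102.19768 + 1.82416 (2) + 0.12776 (2^2"; the full sum is 109.458, matching the stated 109.46 mmHg.

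**4. Paediatric 5th percentile.** Limit = μ(age, height Z) − 1.645σ, with σ = 10.7128 (boys) and 10.4855 (girls) from Table 5-7.

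Boy aged 2 at median height: μ = 102.198 − 14.593 + 8.177 − 1.275 − 5.530 = 88.98, and the limit is 88.98 − 17.62 = 71.4 mmHg. At height Z −2 the height terms add −5.463 − 0.785 + 0.373 + 0.152 = −5.72, giving 65.6 mmHg. Repeating this:

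| Limit, mmHg | Z 0 | Z −1 | Z −2 | Z −3 |
|---|---|---|---|---|
| Boys, 2 years | 71.4 | 68.5 | 65.6 | 63.4 |
| Girls, 2 years | 71.2 | 69.2 | 67.4 | 65.9 |
| Boys, 3 years | 74.0 | 71.1 | 68.2 | 66.0 |
| Girls, 3 years | 72.7 | 70.7 | 68.9 | 67.5 |
| Boys, 4 years | 75.9 | 73.1 | 70.2 | 68.0 |
| Girls, 4 years | 74.3 | 72.3 | 70.5 | 69.0 |

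The limit is below 70 mmHg for height Z below about −0.5 (boys) or −0.6 (girls) at age 2, about −1.4 at age 3, and −2.1 or −2.3 at age 4. At age 5 it takes about −2.8 or −3.5. From age 6 it stayed above 70 at every height checked, and at ages 12 to 17 the lowest limit down to Z −3 is 80.8. With whole-mmHg readings, 69 is missed only once the limit is below 69, which at age 2 means Z at or below −0.83 (boys) or −1.12 (girls). A boy of 2 at Z −2 with a reading of 66 to 69 is below 70 and not flagged.

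**5. Children exposed.** With ages spread evenly over the year and height Z normal with mean −1 and SD 1.2 (assumption), the limit lies below 70 mmHg for about 51% of 2-year-olds and 26% of 3-year-olds. With mean 0 and SD 1 the shares are about 17% and 4%. These too are shares exposed.

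**The case against.** The strongest reply is that Table 2-4 is built to find treatment-emergent change: it pairs level with change for systolic pressure, diastolic pressure and pulse, and a small drift in a patient who starts low is not what it seeks. That is coherent, and it is why the existing criterion should stay. It does not explain why PR and QRS also get a new-absolute-value criterion and blood pressure does not.

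A reader might infer that shock, or the most serious hypotension, would vanish from the safety report. The documents do not support that:

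- The 80 and 70 mmHg values define decompensated shock only together with impaired perfusion. A bare reading is not shock.
- Protocol 8.4.6 has signs of severe malaria reported as SAEs, and SAP 2.7.1.2 tabulates them.
- By-visit summary statistics remain, and a diastolic flag may fire in the same patient.
- Protocol 9.4.2 plans a listing of all vital signs. The SAP does not say that its narrower listing replaces this one, and its section on changes to protocol analyses is redacted.
- Large adult falls to 90 mmHg or below are always flagged.

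All of this stands and limits the point to the notable-value table and its listing.

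Missed readings should also be few. With baseline mean 110 and SD 12, and within-patient SD 6 to 10 (assumptions), roughly 0.2% to 0.35% of single adult readings would be missed; that figure is sensitive to how within-patient variation is modelled.

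Finally, the supplied protocol (Amendment 2) has no Part C. The SAP rests on protocol version 03, which was not supplied, so the paediatric half is conditional.

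**Conclusion.** The point holds as a limited reporting gap. In adults, new readings below 80 mmHg go unflagged when baseline is 80 to 98 mmHg and the fall is under 20 mmHg. About 2% to 33% of adults would be exposed under the assumed baseline distributions (17% at mean 110, SD 12), and far fewer would have such a reading. The exposed share should not be read as a rate of missed hypotension.

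The Part C version is smaller: a band of a few mmHg below 70, in shorter children of about 2 to 4 years and, at age 5, only the very short. It assumes that the later protocol keeps the 70 mmHg value. Adolescents are not affected at the heights checked.

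No efficacy conclusion depends on this. It is worth changing because the remedy is cheap and makes the table count new very low readings that it now omits.

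**What to change.** Keep the existing criteria and, following the SAP's PR and QRS pattern, add a separate newly occurring absolute category for systolic pressure:

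- Table 2-4: below 80 mmHg.
- Table 2-3: below 70 mmHg, after checking that value in the current protocol.
- State that newly occurring means not already below the limit at baseline; the visible text does not define the term.
- Use the new categories for the notable-patient listing as well as the table.
- Reconcile the SAP's notable-only listing with the listing of all vital signs in protocol 9.4.2.

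These are reporting flags only and change no clinical rule. The cost is two short conditions in the SAP tables and the program, one sentence on listings, and a few more flagged patients in both arms.
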